5.7 Withdrawal of Subjects

Participant withdrawals

We will record termination/withdrawal information for participants who decide to leave the study prior to completing the 3-month follow-up. Participants may leave the study at their own discretion, by contacting the research team and notifying them of the decision to leave the study. If participants wish to become unblinded, research staff will inform them of their treatment allocations at the time participants give notification of their decision to leave the study. Withdrawal from the study will not affect care participants receive at VA facilities. Participants will continue to receive any VA care for back pain that they elect to pursue, in coordination with their providers and VA clinical care processes.

Participants may be withdrawn from the study without their consent if they become incarcerated during the study, or if the researchers feel that the study is in some way negatively affecting the participant's health or wellbeing. Participants may also be withdrawn from the study if they demonstrate threatening behaviors or potentially harmful behaviors towards research study staff. Participants will be withdrawn from the study if they are unable to be contacted and/or unable to complete study assessments for 3 consecutive monthly study assessments. In this case, it is assumed that they do not wish to continue in the study, and further contacts would be intrusive.

Although not considered 'withdrawal' per se, participants who are consented may be subsequently excluded prior to randomization, if they 1) are found to not meet inclusion/exclusion criteria, or 2) fail the run-in period between Visits 1 and 2 (i.e. they cannot be reached by researchers during the run-in period. These exclusions cannot take place after randomization. For the purposes of the Informed Consent form, to simplify understanding for potential participants, we do not distinguish between

withdrawals and these pre-randomization exclusions.

5.0 Reporting

Collection of safety information (monitoring) will be performed by the research staff that administer the assessment questionnaires and facilitate data collection, during data collection. Collection of safety information will also include any ad hoc participant-initiated contacts with the study team, and follow-ups by study staff if tracking the course of any potential complications. We will establish a Data Monitoring Committee (DMC) to oversee study safety data. The DMC is described further below.

We will record any potential complications as adverse events (AEs), defined as any untoward medical occurrence that may present during treatment, but which does not necessarily have a causal relationship with this treatment. We will also record serious adverse events (SAEs). We will complete an AE adverse events form for any AEs that occur during the course of this trial. We will record each event as it happens (or as soon as it becomes known to study research team) and we will follow the AE in subsequent scheduled/completed monthly assessments until resolution, the end of the patient's participation or study completion (whichever occurs first). Study staff will report all AEs to the study PI within 1 business day of learning of the AE. Study staff will also report AEs to the appropriate clinical treating provider (the interventional spine physician for AEs possibly related to medical issues or procedural issues, and the treating psychologist for AEs possibly related to mental health). Study staff will complete and send the AE CRF to the Study PI within 5 business days of learning of the AE. The study staff will be responsible for entering the AE data into the study database within 5 business days of learning of the AE. The study staff will be responsible for entering the AE data into the study database within 5 business days of learning of the AE. Study staff will report the AE to the IRB. AEs will be reported to the IRB at the time of continuing reviews. If appropriate, AEs will be reported to the DMC (as described further below).

- The study team will notify the study PI about any SAEs that occur within 1 business day of learning of the SAE. The study PI will notify the IRB within 5 business days of learning about the SAE. The DMC will review SAEs at their scheduled meetings. All SAEs will be reviewed and clinically evaluated by the treating physician. Subsequent clinical evaluation and any further assessment, that may include laboratory or imaging testing as well as treatment, will be done per clinical standards of care.
- Any death that occurs to a subject during their participation in the study is reportable to the IRB and the DMC. The notification to the DMC and the IRB will include a determination from the study PI as to the likelihood of a relationship to the study procedure.
- A. Definition of an Adverse Event, Anticipated Adverse Event and Serious Adverse Event

An **adverse event (AE)** is any untoward medical occurrence that may present during treatment, but which does not necessarily have a causal relationship with this treatment. It can therefore be any unfavorable and unintended event (such as an abnormal laboratory finding), symptom, or disease temporally associated with research participation, whether or not related to research participation.

Anticipated AEs/potential AEs are those which might reasonably be expected to occur from LRFA or simulated LRFA with targeted steroid injections. These might include, but are not necessarily limited to:

• Pain treatment-related: pain at the procedure site, increased pain in low back pain or nerve pain

- Neurological: paralysis, temporary weakness or numbness in legs, dysesthesias or allodynia
- Hypersensitivity reactions to the medications used during the procedure (e.g. anesthetic, or sedative): respiratory or cardiac reactions, seizures, allergic reaction, serious and occasional fatal hypersensitivity (anaphylactic) reactions
- *Endocrine:* short-term increases in blood glucose levels may occur with one-time administration of corticosteroid, in patients with diabetes
- Infection
- Cardiovascular: bleeding at the incision site, injury to blood vessels, clotting of veins
- Vasovagal reaction, hypotension (low blood pressure) (these occur only intra-procedure or immediately after the procedure)
- Miscellaneous: Swelling and bruising at the incision site

Anticipated AEs following prolonged fluoroscopy (X-ray) might include: hair loss, skin redness, and skin damage.

A serious adverse event (SAE) is defined as any untoward medical occurrence that:

- Results in death
- Is life-threatening (Note: the term life-threatening in the definition of "serious" refers to an event in which the patient was at risk of death at the time of the event; it does not refer to an event which hypothetically might have caused death if it were more severe).
- Requires inpatient hospitalization or prolongation of existing hospitalization.
- Results in persistent or significant disability/incapacity.
- Results in congenital anomaly/birth defect (if exposure to a medical product prior to conception or during pregnancy may have resulted in an adverse outcome in the child).
- Requires intervention to prevent permanent impairment or damage.
- Important medical events that may not result in death, be life-threatening or require hospitalization may be considered a SAE when, based on appropriate medical judgment, they may jeopardize the patient and may require medical or surgical intervention to prevent one of the outcomes listed in this definition.

In the proposed trial, the following events are **considered SAEs**:

- Neurologic: paralysis, stroke, central nervous system infection
- Serious hypersensitivity: anaphylactic reactions
- Death
- An event that is life threatening, is permanently disabling, or requires inpatient hospitalization

Severity of adverse event grading scale:

- Mild: an experience that is usually transient, and requires no special treatment or intervention
- Moderate: an experience that is alleviated with simple therapeutic treatments
- Severe: an experience that requires more than simple therapeutic interventions

Relationship to research participation AEs:

- Unrelated This causal relationship is assigned when the AE is definitely not associated with the research participation/treatment
- Unlikely This causal relationship is assigned when there is no temporal relationship to the administration of the investigational material or other factors are more likely to have caused the

event.

- Possibly related This causal relationship is assigned when the AE starts at a reasonable time after study participation but could have been produced by the subject's clinical state or other modes of therapy administered to the subject.
- Probably related This causal relationship is assigned when the adverse event starts at a reasonable time after study participation, stops/improves when study participation/treatment has been stopped, and cannot be reasonably explained by known characteristics of the clinical state.
- Definitely related This causal relationship is assigned when the adverse event starts at a reasonable time after study participation/treatment, stops/improves when study participation/treatment has been stopped, can reasonably be explained by known characteristics of the study participation/treatment.

B. Determination of an Adverse Event

AE identification

We will monitor for adverse events during the entire duration of each patient's participation, including all scheduled/completed monthly assessments and reporting offered by participants during unplanned contacts. In the proposed trial, there are two methods for AE identification: active and passive.

Active identification

Patient Reported: At scheduled study assessments, research staff will inquire about medical/adverse events including surgery, ED visits, hospitalizations and ICU admissions, and allergic reactions. When a patient reports any of the medical events listed above, study research staff will complete an Adverse Event form (Attachment V – Adverse Event Form) and ask the patient details about the event. Such information will include, at a minimum, the date of the event, event seriousness, event treatment and event outcome. Assessments of AEs will include an open-ended question: "Did you experience any other complications?" We will treat any response to these questions as if it is an AE until the study PI can further review and discuss it with the study team if needed.

Passive identification

Medical records review: We will monitor medical records for SAEs at the time of scheduled assessments (monthly) until the end of the 3-month data collection, or longer if a participant elects to continue with optional study assessments after 3 months. If we identify an SAE, the study coordinator will complete an AE CRF and inform the study PI. The list of SAEs to be checked for monthly include: a major neurologic event (paralysis, stroke, central nervous system infection), serious hypersensitivity/ anaphylactic reactions, death, a life-threatening or permanently disabling event, or one that requires inpatient hospitalization.

AE attribution and outcome

The study PI will review all AEs to determine study relatedness and outcome of the event. If the PI is not available, AEs that are more pertinent to medical issues or procedures will be reviewed by [name] or [name], and AEs that are more pertinent to mental health will be reviewed by [name].

C. Other reporting

We will complete an AE CRF for any AEs that occur during the main 3-month follow-up period of data collection. We will record each event as it happens (or as soon as it becomes known to study research team) and we will follow the AE at subsequent scheduled/completed monthly assessments, the end of the patient's participation in the study or study completion, or until directed by the participant's treating provider (treating interventional spine provider or treating psychologist) that the AE has resolved or further tracking is not needed (whichever of these occurrences happens first). Study staff will report all AEs to the study PI within 24 hours of learning of the AE. Study staff will complete and send the AE CRF to the Study PI within 5 business days of learning of the AE. The study staff will be responsible for entering the AE data into the study database within 5 business days of learning of the AE. Study staff will requirements for the reporting AE (see below including UAPs), will report the AE to the DMC and/or IRB.

Unanticipated problems (UAPs) are any problem that is 1) unexpected given the research procedures and subject population, 2) related or possible related to participation in the research, and 3) that may have placed participants at a greater risk of harm than was previously recognized. Harm can be further classified as potential harm or actual harm. The study team and/or PI will report any UAPs to the IRB within 5 business days of learning about the AE that was later classified as a UAP. If serious, we will report this using the form " Report of Unanticipated AND Related Serious Adverse Event (SAE), Unanticipated AND Related Adverse Device Effect (ADE), and/or Unanticipated AND Related Problem Involving Risk to Subjects or Others (UPIRTSO)" (Attachment W – Serious Adverse Event Form). UAPs encompass 'unexpected AEs' and are reported similarly. The DMC will review UAPs that are serious at their meetings.

All AEs, UAPs, and SAEs will be clinically reviewed by a study physician (Drs. [name], [name], [name], or [name] as described above) and clinically evaluated and treated as needed, depending on the problem at hand.

The study team will notify the study PI about any expected or unexpected SAEs that occur within 24 hours of learning of the SAE. The study PI will notify the IRB within 5 business days of learning about the SAE. The DMC will review SAEs at their meetings. All SAEs will be reviewed and clinically evaluated by the treating physician.

Any death that occurs to a subject during their participation in the study is reportable to the IRB. The study PI will report the event to DMC, and to the study sponsor RR&D according to the timeframes of required reporting. The notification to the DMC and IRB will include a determination from the study PI as to the likelihood of a relationship to the study procedure.

D. Safety monitoring

The DMC will review the accruing data to: 1) ensure that study conduct, enrollment, and patient followup is adequate; 2) ensure that there are no serious safety concerns; and 3) assess evidence related to the study outcomes. The DMC will convene every 4 months during active recruitment, and in ad hoc meetings as needed. A report will be compiled for each DMC meeting that will outline study progress including recruitment, retention, protocol violations, AEs, SAEs, and unanticipated problems. In addition, the DMC members will be notified of individual SAEs on an on-going, real-time basis. DMC members will also be sent a "complete" safety and efficacy data report after the first 10 subjects have completed 3-month follow-up, and at the end of data collection for the full expected sample size of 20 participants completing the main 3-month follow-up outcomes. In these "complete" safety and efficacy data reports, we will use a Fisher's exact test to formally compare the event rates between ITT treatment groups and will qualitatively compare to established normative rates. Due to the number of statistical comparisons expected to be made, we do expect to see some differences of p<0.05 for some types of events, so we stress the *gualitative* nature of these comparisons. Based on the currently published data, we anticipate that AEs in the LRFA arm may be more common than in the simulated RFA arm. If there is a qualitative difference in the proportion of SAEs occurring between the study groups and there are concerns regarding the negative effects of the intervention, then the research team in consultation with both the study statistician and the DMC may recommend protocol changes or discontinue the study.

E. Withdrawal of subjects due to adverse effects

We will maintain in the study participants who develop SAEs that are study-related or not, as well as with severe or moderate study-related events (intention-to-treat), unless participants elect to withdraw from the study.

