After each session of AcTIVE-CBT, therapists will complete a brief checklist to document the content areas covered in each session (see Attachment OO). These checklists will be used to assess the quality of the AcTIVE-CBT treatment and that major content areas have been covered. Checklists will be retained in a locked file cabinet in the therapist's locked treatment room/office until the last treatment session is completed. After the last treatment session is completed, the therapist will send the checklist to research staff using the secure VHA Privacy Act/HIPAA Envelope or fax or encrypted email. If a fax is sent, once the fax receipt has been confirmed at the destination location (confirmed by discussion or email with research staff), the original checklist will be destroyed via placement in a designated shredding bin (by the therapist). If the therapist is located at Seattle campus, the research staff can come to the clinical area for a direct handoff of the checklist.

Checklists will be collected by research staff and used to track treatment quality/content covered for each participant. These checklists will be treated in the same manner as study questionnaires, using the same methods for data security.

Table 1: Overvi	ew of Content in AcTIVE-CBT and TBSC	E treatments*
	AcTIVE-CBT	TBSCE
General descriptions and content prior to first session with psychologist	All sessions conducted by video telehealth and psychologist-delivered. Participant will receive basic instruction on Fitbit Zip use from research staff prior to randomization. Participant will receive ongoing research staff support regarding Fitbit use post- randomization, including telephone contacts by research staff at approximately 2 weeks, 6 weeks, and 10 weeks post-randomization.	TBSCE is an active yet lower-dose intensity treatment as compared to AcTIVE-CBT. TBSCE will include pain education and CBT-related education and guidance through [name] CBT ' Managing Chronic Pain ' workbook (referred to as '' Caudill' below) Participant will receive basic instruction on Fitbit Zip use from research staff prior to randomization. Participant will receive ongoing research staff support regarding Fitbit use post-

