- iii. Participants who do wear their Fitbit unit on at least 3 of 7 days during the test period, for 6 hours at least each day during the participant's regular waking hours will be classified as being 'Fitbit-complaint'. Participants who do NOT wear their Fitbit unit on at least 3 of 7 days during the test period, for 6 hours at least each day during the participant's regular waking hours will be classified as 'non-Fitbit compliant'.
- iv. Participants who cannot be contacted at least once during the run-in period will be considered to have failed the run-period. They will be excluded from study participation and will not be randomized.

D. Reassessment of study criteria on the day of randomization (Visit 2):

- i. Initial Screening Criteria will be repeated, as per Table 4 (but not including MBBs). Individuals who no longer meet screening criteria will not be randomized and will not be followed further as part of the study.
- ii. Randomization will take place as described further below.
- iii. The lumbar procedure (LRFA or simulated LRFA) will be performed as per the processes described below.
- iv. Subjects will be given a 2nd study participation pledge form. This version of the pledge form will include the items listed on the 1st pledge form, without information pertinent to the run-in period, but will also include additional details that are specific to each participant's CBT allocation (AcTIVE-CBT vs. TBSCE). Specifically, the AcTIVE-CBT pledge form will encourage the participant to use their Fitbit, and try to gradually increase their daily walking while in the study (Attachment O Pledge Visit 2 Extended). As previously, subjects will have a chance to read the pledge and ask questions, and confirm verbally that they understand the pledge and agree to its content. The participant can keep the pledge form. TBSCE participants will also read a pledge form (Attachment N Pledge Visit 2 Brief), which is the same as (Attachment O Pledge Visit 2 Extended), except it does not specifically encourage active Fitbit engagement, and recommends against using the Fitbit Group or Friend functions.
- v. At the time the 2nd study pledge form is provided by a research staff member, the staff member will will ask the "Post-procedure questions". These involve 1-4 questions, which inquire about the participant's immediate impression of whether they received LRFA, or simulated LRFA.
- E. Approach Letters.

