If Visit 1 is conducted in-person after the 2^{nd} set of MBBs, research staff will also make a brief followup phone call at least 2-5 days after the 2^{nd} set of MBBs, to ascertain the duration of low back pain relief after the 2^{nd} set of MBBs (Attachment L – Screening Checklist, question 21). This brief phone call will last <5 minutes. VISIT 2 (taking place on the same day as the LRFA or simulated LRFA with targeted steroid injections procedure, before the procedure) (20-30 mins duration)

Study assessments for Visit 2 will be conducted in person. Participants will answer questions (Attachment Q - Survey Visit 2) including the RMDQ, low back pain NRS, other pain questions, PROMIS SF-10, and medication use.

VISITS 3-4 (taking place 1 month and 2 months after your procedure (10-15 mins duration)

Table 5*	Screening & Baseline	Treatment	Optional
Study Phase			

Study assessments for Visit 3-4 will be conducted by telephone, unless a participant prefers to have these conducted in person at the Seattle campus. Participants will answer questions (Attachment R – Survey Visit 3_4) including the RMDQ, low back pain NRS, Global Perceived Effect and Satisfaction, medication use, and adverse event reporting.

VISIT 5 (taking place 3 months after your procedure (20-30 mins)

Study assessments for Visit 5 will be conducted by telephone, unless a participant prefers to have these conducted in person at the Seattle campus. Participants will answer questions (Attachment U – Survey Visit 5) including the RMDQ, low back pain NRS, other pain questions, PROMIS SF-10, Global Perceived Effect and Satisfaction, medication use, and adverse event reporting.

Visit Number/Name	1/Final Screen and Consent	2/ Baseline	3/ Month 1	4/ Month 2	5/ Month 3 (1º outcome)	Interim	6-14
Visit Timeline**	-1 to -4 wks.	0	1 mo.	2 mo.	3 mo.	3-6 mo.	Monthly
Length of Visit (min.)	60-70	20-30	10-15	10-15	15-20	10-15	10-15
Informed Consent	\checkmark						
Randomization		~					
LRFA vs. Simulated LRFA Procedure		~					
Sociodemographics	\checkmark						
Roland-Morris Disability Questionnaire and Physical Activity	~	~	~	~		-	~
Low Back Pain NRS	\checkmark	-	~	-	-		
Average Opioid Use	\checkmark	-		-	-		
Other Pain Questions		-			-		
PROMIS SF 10		-			-		
Global Perceived Effect and Satisfaction			~	~	A		~
Self-reported Medications		-	~	-	~	\checkmark	\checkmark
Adverse Event Reporting		\checkmark	~	~	~	\checkmark	~
Compensation	\$35	\$25	\$10	\$10	\$25	\$10	\$10

Interim Study Visit

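### No adverse-event question is described between the procedure and month 1, and most anticipated procedural events have no named prompt, so brief non-serious events may be under-counted

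*Combined protocol and SAP*

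**What the plan says.** Section 5.0, part B, describes active identification of AEs: "At scheduled study assessments, research staff will inquire about medical/adverse events including surgery, ED visits, hospitalizations and ICU admissions, and allergic reactions". It adds an open question on other complications. Passive identification is a monthly record review, limited to serious AEs (SAEs).

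Section 5.5 places the Visit 2 assessment on the procedure day, before the procedure, and gives its content as "including the RMDQ, low back pain NRS, other pain questions, PROMIS SF-10, and medication use". The next assessments are "VISITS 3-4 (taking place 1 month and 2 months after your procedure (10-15 mins duration", with content "including the RMDQ, low back pain NRS, Global Perceived Effect and Satisfaction, medication use, and adverse event reporting". The AE item asks about events since the procedure day. Table 5, as it reads in the copy reviewed, ticks AE reporting at Visit 2 as well as at months 1, 2 and 3.

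Section 5.0, part A, lists the anticipated procedural AEs in eight groups. One is "Vasovagal reaction, hypotension (low blood pressure) (these occur only intra-procedure or immediately after the procedure".

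Two earlier research-staff contacts are described, neither with an AE item. After the procedure, staff ask one to four questions "which inquire about the participant's immediate impression of whether they received LRFA, or simulated LRFA" (Section 5.2, D, item v). Table 1 gives both behavioural arms "telephone contacts by research staff at approximately 2 weeks, 6 weeks, and 10 weeks post-randomization", for Fitbit support.

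There is also an unsolicited route. Participants are told at consent that they may phone in AEs at any time after the procedure day (Section 5.5), and events are to be recorded as they become known (Section 5.0).

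**The concern.** The anticipated events are mostly early, brief and non-serious, while the described enquiry is late, leans towards serious events, and leaves the rest to one open question. A participant who had an hour of leg numbness, a few days of extra soreness at the site or a bruise is first asked about it a month later, without being asked about it by name. By then the participant has also been asked to guess the procedure received, so recall is open to expectation.

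Section 5.0, part D, uses these data twice: Fisher's exact test between intention-to-treat groups, and a comparison with normative rates. The plan expects more AEs with LRFA than with simulated LRFA. If early events are missed in both arms, the absolute difference shrinks and both arms look safer against the norms. Because the pilot exists to inform a larger trial, under-counted rates could also carry forward into that trial's safety planning.

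**Working it through.** The protocol states no AE rate, AE power or AE sample size, so there is no figure to reproduce. The check is mainly a comparison of passages.

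**When AEs are asked about.**
- Day 0, before the procedure: Visit 2 assessment, no AE item in the text.
- Day 0, after the procedure: pledge form and blinding-guess questions, no AE item described.
- About day 14: staff Fitbit call in both behavioural arms, no AE item described.
- About day 30: Visit 3, first described AE enquiry, covering the time since the procedure day.

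The Table 5 tick at Visit 2 does not settle the matter. The AE item covers events since the procedure day, so a question put before the procedure would have nothing to cover. Either the tick stands for a same-day post-procedure question that no text describes, or it is an error.

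**Recall interval.** About 30 days now. With an AE question on the 2-week call it is about 14 days: 14/30 = 0.47 of the present interval. Against a stated duration of minutes to hours (risk description, Section 5.1) even 14 days is long, so the same-day question matters most for immediate events.

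**Prompts against anticipated events.** The eight groups are: pain; neurological; hypersensitivity; endocrine (glucose); infection; cardiovascular (bleeding, vessel injury, clots); vasovagal reaction or hypotension; swelling and bruising. The named prompts are surgery, ED visits, hospitalization, ICU admission and allergic reactions. Only the allergic part of the hypersensitivity group matches. Serious forms of the others would be reached through the hospital prompts or record review; non-serious forms would not.

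**Events during the procedure.** These are seen by the second attending and the clinical assistant. Section 5.1 describes the second attending as not involved in data collection, and no step moves an event from the procedure note to the AE form.

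**Illustration of size.** Assume 20 completers split 10 and 10 on the procedure factor, and the same capture fraction c in both arms. The observed difference is c × (p1 − p2). The ratio p1/p2 is unchanged.

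| Assumed true rates | Capture c | Expected counts of 10 | Observed difference | Fisher power, two-sided 0.05 |
|---|---|---|---|---|
| 60% vs 20% | 1.00 | 6.0 vs 2.0 | 0.40 | 25% |
| | 0.75 | 4.5 vs 1.5 | 0.30 | 14% |
| | 0.50 | 3.0 vs 1.0 | 0.20 | 6% |
| | 0.25 | 1.5 vs 0.5 | 0.10 | 1% |
| 80% vs 20% | 1.00 | 8.0 vs 2.0 | 0.60 | 64% |
| | 0.75 | 6.0 vs 1.5 | 0.45 | 35% |
| | 0.50 | 4.0 vs 1.0 | 0.30 | 15% |
| | 0.25 | 2.0 vs 0.5 | 0.15 | 2% |

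The smallest split from zero that reaches p < 0.05 is 0 vs 5: p = 2 × C(10,5)/C(20,5) = 2 × 252/15504 = 0.033. For 0 vs 4, p = 2 × C(10,4)/C(20,4) = 2 × 210/4845 = 0.087. The test is weak even with full capture, so the main loss is in the estimated rates and differences rather than in a p-value.

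**The case against.** Several stronger readings are tempting, and the documents do not support them.

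- *A reader might infer that no AE question of any kind exists before month 1.* The Visit 2 column of Table 5 also holds randomization and the procedure, so its tick may cover the whole day. The Visit 2 text list is not exhaustive: it also omits physical activity, which Table 5 ticks. The passages need reconciling; neither can be declared right.
- *That procedural AEs are not prompted at all.* Allergic reactions are both anticipated and prompted, the list opens with 'including', and an open question follows. The survey attachments may hold a checklist. Worsened back pain may also show in the pain rating at Visit 3.
- *That everything rests on recall.* Participants may phone at any time, and staff must record what they learn. For minor events this waits on the participant, so it does not replace asking.
- *That vasovagal events are lost.* Staff in the room see them. What is missing is a described route to the AE form.
- *That the protocol gives these events a duration of days.* It gives minutes to hours, or calls them temporary or short-term.
- *That the Fisher comparison is the sole safety safeguard.* The Data Monitoring Committee meets every 4 months and is told of SAEs in real time. The protocol stresses that the AE comparisons are qualitative and ties possible protocol changes or stopping to SAEs, which record review covers.

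The pain-response calls 2-5 days after each set of medial branch blocks are not safety calls; they show only that early calls are feasible. What stands against the objection is that no text describes a solicited, structured AE question between the procedure and month 1.

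**Conclusion.** The concern holds in limited form. Apart from the unexplained tick in Table 5, the first described AE enquiry after the procedure comes at about 30 days, and seven of the eight anticipated groups, plus the non-allergic part of the eighth, have no named prompt. Under-counting of brief, non-serious events is likely enough to guard against, but it is not established. The documents give no AE or capture rates, and the figures above rest on assumed values and on equal capture in both arms. If capture differed between arms, the bias could go either way. The primary outcome and SAE detection are not affected. The change is worth making because it improves the AE rates that the pilot will report and costs little.

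**What to change.** 1. Reconcile Table 5 with the Visit 2 text, and state whether an AE question is asked on the procedure day and when. Ask a brief one at the existing post-procedure contact, **after** the blinding-guess questions. Have the non-blinded research staff member transcribe intra-procedure events from the procedure note to the AE form, which keeps allocation away from blinded staff.
2. Add the same AE question to the existing 2-week staff call in both behavioural arms, and to the 6- and 10-week calls if wanted, with one script for all participants.
3. At Visits 3-5, ask a short yes/no checklist drawn from the anticipated AEs in Section 5.0, part A, before the open question. If the survey attachments already contain one, say so in Section 5.0, part B.

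Cost: a few minutes per contact, plus edits to scripts, the AE form and Table 5. No new visits or staff are needed. There will be more minor AEs to record. Asking about symptoms on the procedure day carries a small risk of influencing the blinding guess, which is why the order in item 1 matters.
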